ECT = every contraction timed – Indicates that the above scheme is repeated up to 10 repetitions with each there is a determination of power, endurance and repetitions.

A prescription will be provided for each participant based on their individual PERFECT assessment; typically this details numbers of repetitions, duration of squeezes, and numbers of sets. Based on physical therapy and exercise science literature, 8-12 repetitions of 3-4 sets over 6 weeks increases strength and efficiency of muscle recruitment.[23]

All participants will use a calendar to record daily compliance with PFMEs.

E. UI assessment: UI and pelvic floor symptom assessment will be performed by asking for a history of UI symptoms (years), UI treatment, and number of pads used per day for UI. Participants will complete a 3-day voiding diary to record urinary frequency, urinary urgency and incontinence episodes classified by clinical type (urgency, stress, insensible) along with time of occurrence (day, night).[24] This will be returned during week 2 (baseline), week 6, and week 12. UI symptom impact on daily life will be measured subjectively with the QUID and the Pelvic Floor Impact Questionnaire (PFIQ)-Short Form 7.[25] The Pelvic Floor Distress Inventory (PFDI) short-form 20 will be used to

characterize all pelvic floor symptoms (urinary incontinence, fecal incontinence, voiding dysfunction, overactive bladder, and pelvic organ prolapse).[25]

F. Physical function assessment: Participants will undergo the following assessments:

- **Extended version of the Short Physical Performance Battery (expSPPB).** The expSPPB is a standard and robust predictor for disability that includes progressively more challenging standing balance tasks held for 10-30 seconds each (side-by-side, tandem, and semi-tandem, single leg), 4-meter walk to assess usual gait speed, 4-meter narrow walk test of balance, and five chair-stands test.[26, 27] The timed 4-meter walk will be performed as a surrogate for the 6-meter walk; it is associated with urgency/stress UI and its results are strong predictors of falls and fractures in women.
- **Timed 400 meter walk (min:sec) (22)**
- **Isokinetic dynamometer (Biodex®)** as an objective measure of strength, maximal isokinetic knee extensor strength in the right leg will be measured at speeds of 60 degrees/sec. The left leg will be used if the participant has severe knee pain or a joint replacement in the right knee.

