J. Cognitive function will be assessed using the Montreal Cognitive Assessment (MoCA). Mild cognitive impairment will be defined as MoCA score of <26. Severe cognitive impairment will be determined by MoCA score <21.[38]

At the conclusion of the Study Visit 1, participants are given a folder labeled with their study ID. The folder will contain the following:

- Voiding diary (toilet hat should accompany this)
- Pelvic floor muscle exercise compliance log (we explain that this is an observational study, therefore, they should only complete the log reflecting what they actually are able to do at home)
- Copy of informed consent form
- Label indicating the time/day of their next appointment

- Sheet cover insert containing the bladder diary OR questionnaires necessary for the upcoming study visit 2 (bladder diary), study visit 3 and 4 (Questionnaires and bladder dairy)

All assessments will be repeated during the 6- week follow-up visit. Questionnaire based assessments and UI voiding diaries will also be repeated at week 12. (see *Appendix Table 1 – Assessment schedule*)

*We were mailing the questionnaires, but they would invariably reach the participants in time. Therefore, we are modifying our technique to increase compliance with completing the questionnaires and improve the efficiency of study visits.

Study visit 2 (week 2): (20 minutes) This visit will ensure that pelvic floor muscle strength and contractions are being performed and recorded correctly. The PI will assess each participant by performing a digital vaginal exam, to confirm proper isolation of pelvic floor muscles and ability to complete the PFME prescription. The bladder diary will be reviewed, clarified, and collected. A data abstraction form should be completed at this time. The pelvic floor exercise prescription may be modified at this visit, if that occurs, a new document will be provided and the previous prescription will be stored in the participants chart. The PFME compliance log should be reviewed. A brief visit note should be completed to summarize the events.

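### The readable plan does not place the baseline bladder diary before the first exercise session, so the baseline for the primary endpoint can be an on-treatment value

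*Combined protocol and SAP*

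**What the plan says.** The Analytical Plan defines the primary outcome as the percentage reduction in weekly UI episodes at week 6, compared between women with and without functional impairment. Study Design takes the episode counts from the 3-day voiding diary.

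Under study visit 1, section D (Pelvic floor assessment): "A prescription will be provided for each participant based on their individual PERFECT assessment". The same section adds: "All participants will use a calendar to record daily compliance with PFMEs". Section E (UI assessment) says of the diary: "This will be returned during week 2 (baseline), week 6, and week 12".

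The folder handed over at the end of visit 1 holds the diary ("Voiding diary (toilet hat should accompany this") and the exercise log ("Pelvic floor muscle exercise compliance log"). It also holds a "Sheet cover insert containing the bladder diary OR questionnaires necessary for the upcoming study visit 2 (bladder diary"; for visits 3 and 4 the same item lists questionnaires and diary.

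At visit 2 (week 2), "The bladder diary will be reviewed, clarified, and collected". That visit also checks that contractions are being done and recorded properly, and reviews the exercise log.

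The reminder-call paragraph has staff telephone 3 days before visits 2, 3 and 4 about completing the diary. Visit 3 falls 6 weeks after the initial assessment. Appendix Table 1 ticks the diary at Baseline, 6 and 12 weeks but not at 2 weeks. It ticks the exercise log at 2, 6 and 12 weeks but not at Baseline.

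**The concern.** A percentage change from baseline means what the plan intends only if the baseline comes before the treatment. Here the prescription, the log and the blank diary all reach the woman on the same day. The one stated prompt to complete the diary comes at about day 11, and nothing readable asks her to finish it before she starts exercising.

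If exercise has any effect in the first two weeks, the diary used as the denominator already contains part of the gain. Each group's six-week reduction is then understated. That matters directly because the plan hypothesises a 50% reduction by week 6 and intends within-group as well as between-group comparisons. The effect would also differ between women according to when each kept the diary and began exercising, and the plan does not ask for either date. The listed diary content is frequency, urgency and typed episodes, "along with time of occurrence (day, night" only, so calendar dates may not be available afterwards.

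**Working it through.** **1. Order of events in the readable text**

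- Before visit 1: the mailed packet lists the consent form, questionnaires and a letter. No diary is listed.
- Visit 1 (day 0): prescription given; diary and exercise log taken home.
- About day 11 (14 − 3): reminder call to complete the diary.
- Day 14 (visit 2): diary collected as baseline; technique checked; log reviewed. The text allows the prescription to be modified here, with the previous one filed, so a prescription is already in force.
- Day 42 (visit 3): week-6 diary, timed from the initial assessment.

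Exercise is therefore expected between days 0 and 14, and the call steers the diary towards days 11 to 14.

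**2. Passages that could point the other way**

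- *Table 1.* The Baseline tick could mean a diary kept before exercise and merely handed in at visit 2. But the same column holds the PERFECT assessment that generates the prescription, so a tick there does not fix the order of diary and exercise.
- *Calendars at week 6.* Visit 3 asks for four weeks of exercise calendars, which could suggest that counted exercise starts at week 2. Visit 4 asks for six. These match the intervals since the preceding visit: 6 − 2 = 4 and 12 − 6 = 6. That fits a log for weeks 0 to 2 already reviewed at visit 2. If exercise did start at week 2, week 6 would hold about 4 weeks of exercise, against the 6 weeks named in Study Design.

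Neither passage settles the order.

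**3. The plan's own sample-size figure**

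A 20-point difference, SD 32, two-sided 0.05 and 80% power need 41 evaluable women per group. Then 41 / 0.85 = 48.2, so 49 enrolled, against 50 stated. The figure reproduces and is not in question here.

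**4. Size of the understatement within a group (illustration)**

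From the plan: true six-week reduction R = 0.50. Assumptions: exercise starts on day 0, the gain accrues linearly over 42 days, and the diary is treated as if kept on a single day d. With f = d/42 and B the pre-exercise episode rate, episodes at the diary are B(1 − fR) and at week 6 are B(1 − R), so

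measured reduction = 1 − (1 − R)/(1 − fR).

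| Diary day | f | fR | Measured reduction |
|---|---|---|---|
| Before exercise | 0 | 0 | 50.0% |
| 11 | 0.262 | 0.131 | 1 − 0.50/0.869 = 42.5% |
| 14 | 0.333 | 0.167 | 1 − 0.50/0.833 = 40.0% |

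For any early gain above zero, the measured reduction is below the true one.

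**5. Direction for the between-group difference (illustration)**

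Take true reductions of 50% and 30%. The 30% is an assumption (50 minus the planned 20 points), as are all the early gains. With early gain g, measured reduction = 1 − (1 − R)/(1 − g).

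| Early gain (unimpaired, impaired) | Measured reductions | Difference |
|---|---|---|
| none | 50.0%, 30.0% | 20.0 points |
| one third of each group's own gain (16.7%, 10%) | 40.0%, 22.2% | 17.8 points |
| equal 10% in both | 44.4%, 22.2% | 22.2 points |
| 16.7%, 12.5% | 40.0%, 20.0% | 20.0 points |

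The difference can shrink, grow or stay the same.

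**The case against.** The strongest reply is that section E fixes when the diary is returned, not when it is kept, and itself calls it the baseline. In Table 1 the diary has a tick at Baseline and none at 2 weeks, while the exercise log has the reverse. A diary kept in the first days and handed in at visit 2 fits both passages, and a call 3 days ahead could be a prompt to finish it and bring it along. The flow chart is not shown and the diary form is not among the documents; either might state the order.

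Much of this stands. A reader might infer that the baseline is certainly taken on treatment, and the documents do not establish that. They establish that nothing readable prevents it and that the only stated prompt makes it likely. A woman who waited for the call would follow the plan exactly and still produce an on-treatment baseline.

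A reader might also infer that the primary comparison is biased towards no difference or loses power. The documents do not support that either: the result depends on early gains in each group and on how they vary between women, and neither is given. Nor should a wide spread from day-1 to day-14 diaries be assumed, since the call would cluster diaries near days 11 to 14. Under the linear illustration that spread is 42.5 − 40.0 = 2.5 points.

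**Conclusion.** The point holds in this form: as written, the plan allows the baseline of its primary endpoint to be measured after up to about 2 of the 6 weeks of exercise, and its passages on the diary need reconciling. Each group's reduction is understated if there is any early effect. The illustrated size is 7.5 to 10 percentage points on a true 50%, resting on linear accrual, exercise from day 0 and a diary at days 11 to 14. The documents do not give the true early response, so this is not an estimate.

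No direction is claimed for the difference between groups, and no loss of power. The point should be corrected because it affects the meaning of the primary endpoint and is cheap to settle. If the flow chart or diary form already requires the diary before exercise, what remains is to bring the text and the reminder call into line with it.

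**What to change.** 1. Reconcile section E of visit 1, the folder contents, the visit 2 text, the reminder-call paragraph and Table 1 so that the baseline diary, already in the visit-1 folder, is completed after consent and before the first PFME session. Move that diary's reminder call accordingly. Record the diary dates and the exercise start date on the data abstraction form already completed at visit 2, and state from which date week 6 is counted. The exercise prescription stays unchanged.
2. For women already enrolled, where dates exist, report by group how many exercise days preceded the baseline diary. Describe the endpoint as change from an on-treatment week-2 diary only where the dates show this or the order cannot be established.
3. Record which baseline timing each woman had. New screens after amendment 12 must have a Short Physical Performance Battery (SPPB) score of 9 or less. If groups are formed by SPPB, as the recruitment text suggests, a change made now would fall mainly on the impaired group and tie baseline timing to group.

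The cost is protocol wording, one rescheduled call and two data fields, with no added visit. The downside is that exercise may start a few days later.

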AIM 3: To explore the relationship between obesity, attitudes (barriers, motivation) towards physical activity, and physical activity levels in a well-characterized longitudinal cohort of older women with UI symptoms. **Hypothesis 3.** Older women with UI view UI severity as a barrier to a high physical activity. Lower physical activity levels (defined as <6.2 MET hours/week) in women with UI impacts on physical performance and is associated with obesity. Physical activity levels will be determined using the Community Healthy Activities Model Program for Seniors questionnaire that reports metabolic equivalent task (MET) hours/week.(6) Questionnaires will assess barriers to and motivations for physical activity.

METHODS AND MEASURES:

Study Design:

We plan a prospective cohort study with an adaptive design based on physical function status. The design will involve tracking the number of women recruited with physical function impairment and those without any functional impairment. We aim to recruit similar numbers of women in each group. If we find unequal numbers, we will adapt our recruitment strategies based on a woman's functional status.

We will compare changes in outcome measures within and between groups after 6 and 12 weeks of PFME. The change in pelvic floor strength/efficiency will be assessed by repeating the pelvic floor PERFECT assessment and will be compared between groups. Changes in UI symptoms, symptom severity, and impact of UI symptoms on quality of life will be determined using standardized measures described above. Data analysis will define associations between changes in PERFECT measures and the change in UI episodes (based on 3-day voiding diary), severity, and type (based on QUID-7), and impact on quality of life (PFIQ-7) within and between groups. Objective measurement of lower-extremity strength will inform the relationship between lower-extremity strength, pelvic floor strength, and UI symptoms at baseline and the 6-week visit. (See Appendix Figure 1 – Study Flow Chart)

Setting:

Study visits will take place at the Sticht Center on Aging in the Geriatric Research Clinic. The study coordinator will meet the participants in the GRC to confirm eligibility, describe the study, answer any questions, and administer written informed consent.

Subject selection criteria:

- **Inclusion criteria:**
 - a) Women, age 70 years or older
 - b) Symptoms of Urinary Incontinence for greater than 6 months

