- Balance will be measured using a **postural sway test**. Center-of-pressure (COP) trajectory data will be collected using an Advanced Mechanical Incorporated (AMTI) AccuSway biomechanics force platform. Four posturographic parameters (maximum antero-posterior and medio-lateral displacement, average sway velocity, and 95% confidence ellipse) and two statistical mechanics measures (stabilogram diffusion analysis and detrended fluctuation analysis) will be calculated to quantify postural sway according to our previously published methods. [30]

G. Comprehensive prospective evaluation for physical function limitations will be assessed with the Pepper Assessment Tool for Disability (PAT-D) and the Mobility Assessment Tool-Short Form (MAT-SF) to measure activities of daily living disability, mobility disability and instrumental activities of daily living disability to assess changes in disability. The MAT-SF is a novel, computerized tool for self-assessment of functional performance designed to reduce bias from factors such as age, gender and body image.[31] [32]

H. Sarcopenia will be determined using the following validated questionnaires and objective physical function measures with standard cut-offs:

- Grip-strength and gait speed will objectively measure weakness.[33]
- The “SARC-F” is a short-form questionnaire validated to identify adults with sarcopenia and who are at risk for adverse outcomes and may benefit from a physical function intervention. [34]
- Whole-body DEXA scans will be used to calculate the appendicular lean muscle mass.[35, 36]

I. Physical activity will be assessed using the Community Healthy Activities Model Program for Seniors (CHAMPS) questionnaire assesses weekly frequency and duration of various physical activities common to older adults to evaluate the efficacy of behavioral interventions aimed at increase levels of physical activity. Caloric expenditure (MET hours/week) will be reported.[8] 'Low activity' will be defined as <6.2 MET-hours/week of activity. Women with 6.3-11.4 MET hr/week will be classified as having low-moderate activity. Since only 23% of incontinent women had >11.4 MET hours/week of physical activity, this level will be defined as high activity.[8] Validated questions will be asked to identify potential barriers to physical activity related to UI symptoms.[37]

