400 meter walk (min:sec)	The 400m walk is a direct measurement of exercise tolerance AND correlates with measured VO ₂ peak.[41]
Isokinetic dynamometer (Biodex®)	As an objective measure of strength, maximal isokinetic knee extensor strength in the right leg will be measured at speeds of 60 degrees/sec. The left leg will be used if there is a reason not to measure the right leg.
Postural Sway	Center-of-Pressure (COP) trajectory data will be collected using an Advanced Mechanical Incorporated (AMTI) AccuSway biomechanics force platform. Participants will be barefoot in an upright stance with arms raised comfortably at their sides, feet abducted, and heels separated. Four posturographic parameters (maximum antero-posterior and medio-lateral displacement, average sway velocity, and 95% confidence ellipse) and two statistical mechanics measures (stabilogram diffusion analysis and detrended fluctuation analysis) will be calculated to quantify postural sway according to our previously published methods.
Sarcopenia measures	
Grip-strength	As an objective measure of weakness and marker of sarcopenia.[33]
Gait speed	Determined based on 4-meter walk at usual speed as a marker of sarcopenia.[35]
SARC-F	The SARC-F questionnaire is validated to identify adults with sarcopenia and who are at risk for adverse outcomes and may benefit from a physical function intervention. [34]
Whole Body DEXA scan Time:	The appendicular lean muscle mass/height will be calculated based upon a whole-body DEXA scan performed in the Geriatric Research Unit.
Physical Activity Assessments	
Community Healthy Activities Model Program for Seniors (CHAMPS) questionnaire	The CHAMPS questionnaire is a brief valid measure that assesses weekly frequency and duration of various physical activities common to older adults to evaluate the efficacy of behavioral interventions to increase levels of physical activity. Caloric expenditure (MET hours/week) will be reported.[8] 'Low activity' will be defined as <6.2 MET-hours/week of activity. Women with MET hr/week between 6.3 and 11.4 will be classified as low-moderate activity. Since only 23% of incontinent women had >11.4 MET hours/week of physical activity, this level will be defined as high activity.[8]
Barriers to physical activity questionnaire	Questions regarding attitudes towards physical activity considering UI symptoms and perceived barriers will be assessed.
Comprehensive prospective evaluation for physical function limitations	

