The hypothesis for AIM 1 (Primary) will be tested using analysis of covariance (ANCOVA) to compare differences of efficacy of PFME therapy (i.e. % UI episodes/week reduction at week 6) between women with and without functional impairment, adjusted for age, race/ethnicity, and BMI. Differences in least-squares means and associated 95% confidence intervals will be calculated. For Sub-aim 1(a), attitudes (barrier and motivation) towards physical activity will be compared between higher vs. lower physically active women using Chi-Square tests. For Sub-aim 1(b), association between physical activity (lower vs. higher) and UI severity will be tested using logistic regression, adjusting for age, race/ethnicity and BMI. Odds ratio and associated 95% confidence intervals will be calculated. We will also explore the impact of functional impairment on the association by adding an interaction of functional impairment and UI severity. Similar ANCOVA models as for Aim 1 will be used to compare efficacy of PFME therapy between women with and without sarcopenia (AIM 2) and between women with and without mild cognitive impairment (Aim 3).

Potential Pitfalls and Alternative Solutions:

- a) **Recruitment:** Women will be recruited from the community in the catchment area for Wake Forest Baptist Health system, which includes central and western North Carolina and south central Virginia. Last year, we saw 476 women with a urinary incontinence diagnosis. More than 30% of women older than 70 have UI symptoms and an equal number will have functional impairment. Therefore, we do not expect difficulty in recruiting 50 eligible women/year over 24 months. The Wake Forest Sticht Center on Aging has an established database of older volunteers for aging-related research (VITALS database=12,600) that will also be a source of recruitment. If necessary, we may start targeted recruitment to ensure that ~ 50% of potential participants have a SPPB score > 10 and that 50% have scores of ≤ 9 .
- b) **Adherence to PFME therapy:** Participants will receive a calendar with their PFME prescription on it and places on the calendar to document compliance. They will be contacted by study staff every 2 weeks to assess for compliance and to reinforce adherence to therapy. This approach has resulted in good compliance in other trials of elderly adults run by the Sticht Center.

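### Sub-aim 1(b) cuts continuous activity into two groups, losing at least about a third of its information, and the obesity and performance parts of Hypothesis 3 have no named analysis

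*Combined protocol and SAP*

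**What the plan says.** The section Analytical Plan & Statistical considerations states for Sub-aim 1(b) that the "association between physical activity (lower vs. higher) and UI severity" will be examined by logistic regression, adjusted for age, race/ethnicity and BMI. As an exploratory step it proposes "adding an interaction of functional impairment and UI severity". Sub-aim 1(a) uses the same two activity groups in Chi-Square tests of attitudes. No MET value appears in that section.

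The values are elsewhere:

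- Objectives, Hypothesis 3: "Lower physical activity levels (defined as <6.2 MET hours/week) in women with UI impacts on physical performance and is associated with obesity".
- Outcome measures table, CHAMPS row (also Study visit 1, item I): low activity is below 6.2 MET-hours/week. For the middle level, "Women with MET hr/week between 6.3 and 11.4 will be classified as low-moderate activity". For the top level, "Since only 23% of incontinent women had >11.4 MET hours/week of physical activity, this level will be defined as high activity".

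The same CHAMPS entries say that energy expenditure will be reported in MET-hours per week. The analysis that the analytical plan labels Aim 3 compares exercise efficacy between women with and without mild cognitive impairment. The Aim 3 set out under Objectives concerns obesity, attitudes and activity.

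**The concern.** Two things look wrong, and they are separate.

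First, a measured continuous variable becomes a binary outcome. That discards information in a study of about 100 women for which no power is stated on this question. The link from three levels to two is also left to inference. The wording of Hypothesis 3 points to 6.2, but a reader could take the higher group to be the defined high level, above 11.4. Fixing the choice before the data are seen costs nothing. The Chi-Square tests of Sub-aim 1(a) depend on the same choice.

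Second, part of a stated hypothesis may never be estimated. Hypothesis 3 asserts that low activity "impacts on physical performance and is associated with obesity", and the analytical plan names no analysis that answers either half of that statement.

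**Working it through.** **The plan's own power figure.** The documents give none for Sub-aim 1(b). The only one, under Sample Size Estimate, is for the comparison of improvement in UI episodes: 50 per group, 15% dropout, difference 20%, SD 32%, two-sided 0.05, at least 80% power. It reproduces: n = 2 × (1.96 + 0.8416)² × (32/20)² = 40.2, so 41 per group, and 41/0.85 = 48.2, so 49 against the 50 planned. It does not bear on the activity analysis.

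**Information kept by a single cut.** Assume that activity is normal after a suitable transformation and that its association with UI severity is weak and linear. If a share p lies on one side of the cut, then

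efficiency = φ(z_p)² / [p(1 − p)],

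where z_p is the normal quantile and φ the normal density. The smallest correlation detectable at 80% power (two-sided 0.05, unadjusted) is (1.96 + 0.8416)/√(N × efficiency).

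| Share on one side of the cut | Efficiency | Loss | Detectable r, N = 100 |
|---|---|---|---|
| No cut (continuous) | 1 | 0 | 0.28 |
| 50% | 0.637 | 36% | 0.35 |
| 40% or 60% | 0.622 | 38% | 0.36 |
| 30% or 70% | 0.576 | 42% | 0.37 |
| 23% or 77% | 0.521 | 48% | 0.39 |
| 20% | 0.490 | 51% | 0.40 |
| 10% | 0.342 | 66% | 0.48 |

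As a worked line, p = 0.5 gives 0.3989²/0.25 = 0.637, and 2.8016/√63.7 = 0.351. The median split is the best case, so 36% is the minimum loss under these assumptions.

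At N = 85 (100 less 15% dropout) the detectable correlations are 0.30 continuous, 0.38 at a median split and 0.42 at 23/77. For an assumed correlation of 0.30 with N = 100, power is 85%, 67% and 58% in the same order.

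**Which row applies.** The documents do not give the share below 6.2, so this plan's loss is a range: 36–42% if that share is 30–70%, about 51% if it is 20%, and about 66% if it is 10%. The 23% in the documents is a cited external share above 11.4. It would apply only if the cut were 11.4 and this cohort matched the source.

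**Sensitivity to the normal scale.** Suppose MET-hours are lognormal (assumed log-SD 0.5 to 1.0) and the relation is linear on the raw scale. The loss is then 39–55% with 23% above the cut and 49–73% at the median.

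**Hypothesis 3 against the analytical plan.**

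| Part of Hypothesis 3 | Planned analysis |
|---|---|
| UI severity as a barrier to high activity | Sub-aims 1(a) and 1(b) |
| Low activity affects physical performance | None. Functional impairment enters only as an exploratory modifier of the UI severity effect |
| Low activity is associated with obesity | None named. BMI is an adjustment covariate |

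**The case against.** The strongest objection is that the cut is stated. Hypothesis 3 defines lower activity as below 6.2, the analytical plan uses the same word, and the complement then takes in the low-moderate women. This stands. A reader might infer that the plan has no cut at all, and the documents do not support that. What is missing is a cross-reference in the analytical plan, an explicit mapping of three levels to two, and a category for values from 6.2 to just under 6.3.

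A reader might also combine the 23% with 100 women to get 23 in the smaller group, spread them over seven parameters, and report 23/7 = 3.3 events per parameter. That does not hold either. It needs the 11.4 cut rather than 6.2, borrows an external share, and counts the exploratory interaction model. The main model has UI severity, age, BMI and one or two race/ethnicity terms, so four or five parameters. Even 23 events would give 23/5 = 4.6 to 23/4 = 5.8. With the share below 6.2 unknown, no event count for this plan can be computed.

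It is also fair to say that an odds ratio for low activity is easy to read, that the aim is framed as exploratory, and that the fitted model would print a BMI odds ratio anyway. The first two limit the weight of the point. The third is only partly an answer: the plan does not name that coefficient as a result, and nothing comparable exists for physical performance. The general provision for transforming data does not change the choice of a binary outcome.

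**Conclusion.** The point holds, in two parts.

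- **Dichotomising.** Under approximate normality after transformation and a weak linear association, any single cut loses at least about 36% of the information on activity, and adopting 6.2 explicitly does not remove that loss. With 100 women the detectable correlation rises from about 0.28 to 0.35 or more. The 48% loss belongs only to a cut at 11.4 with the external 23% above it, and should not be read as this plan's figure.
- **Untested parts of Hypothesis 3.** No planned analysis has physical performance as an outcome of activity, and none names obesity as a result. This rests on the text alone and needs no distributional assumption.

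The change should be made, but its weight is limited: the aim is exploratory, no power is claimed for it, and the primary ANCOVA of reduction in UI episodes at week 6 is unaffected.

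**What to change.** In the analytical plan:

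1. Make the main Sub-aim 1(b) analysis a linear regression of MET-hours/week on UI severity, with the same covariates and the same exploratory interaction. Use a transform that allows zeros, such as the square root or log(x + 1), and fix it in advance.
2. Name the activity–BMI association as the obesity result of Hypothesis 3.
3. Add models of SPPB and of 400-m walk time on MET-hours, with the same covariates, as the performance result.
4. Keep the binary odds ratio as a secondary, descriptive result. Cite the 6.2 cut from Hypothesis 3, state that low-moderate women then fall in the higher group, and use the same rule in Sub-aim 1(a).
5. Close the categories as below 6.2, 6.2 to 11.4, and above 11.4.
6. Align the Aim 3 label between the Objectives and the analytical plan.

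The cost is wording only. CHAMPS, BMI, SPPB and the 400-m walk are all in the baseline column of Appendix Table 1. The downside is that an effect on a transformed scale is harder to state than an odds ratio, which is the reason to keep the binary result beside it.
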